All things considered, the thorough examination of the exclusions, withdrawals, and reported adverse effects in the pooled analysis sheds light on the difficulties and conclusions that have been found in a number of research. It emphasizes how crucial it is to closely monitor participant outcomes and unfavorable occurrences in clinical research in order to guarantee the efficacy and safety of the medicines being studied(30).

The treatment for distal ureteral stones with size less than 10 mm with tamsulosin and silodosin has resulted in a high output rates of 57-64% and 80 - 84%, respectively, according to randomized controlled studies. Nonetheless, compared to other trials, the tamsulosin success rate in those investigations is somewhat lower (31). However, tamsulosin demonstrated an 86% success rate in a randomized controlled study with almost 3000 patients(32). Tamsulosin has a 67–90.7% success rate in treating distal ureteral stones, according to Tao

et al.'s meta-analysis.20 The current study's tamsulosin success rates align with some studies (33).

Similar to the current investigation, the comparable rates in the Imperatore et al. study were 82% and 88%, and in the Arda et al. study they were 72.4% and 78.6%. These investigations also revealed no discernible difference between tamsulosin and silodosin. However, only young/middle-aged men were included in this study, whereas both of other investigations included both men and women. This sums up the main distinction between prior studies and the present investigation (34).

Tamsulosin is used commonly in our population for MET however Silodosin, a newer drug, is not used frequently for this purpose and is still under research. Also, comparison of Silodosin and Tamsulosin has not been explored in our population earlier.

Rationale

The purpose of this study is to examine and compare the effectiveness of silodosin and tamsulosin in medical expulsive therapy (MET) in terms of the rate at which stones are expelled from the body, as well as the adverse effect profiles in our patient group.

OBJECTIVES:

To evaluate and compare the efficacy and safety of medical expulsive therapy containing tamsulosin and silodosin, specifically.

To compare the side effect profile of tamsulosin and silodosin when given for medical expulsive therapy.

HYPOTHESIS:

Null Hypothesis:

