- Bleeding disorders
- Obstruction distal to stone
- Serum Creatinine > 1.3 mg/dl in males and > 1.2 mg/dl in females.
- Congenital renal anomaly/ skeletal malformation
- Previous treatment for the same stone (PCNL/ URS / push back)
- Solitary Kidney
- Prior JJ stent insertion
- Bilateral ureteral stone

DATA COLLECTION AND PROCEDURE:

The protocol will be submitted to Ethical review committee for review and only once the permission is granted, the study will be started. Patients will undergo standard procedure like detailed history taking, examination and routine investigations. Once decided that the patient will undergo MET, the patient will be explained in detail about medications, their potential side effects, follow up and the potential indications for early follow up. Our study will not change any standard process in place except the randomization between Tamsulosin and Silodosin. The data will be kept confidential as a top priority. Only principal investigator and co-principal investigator will have access to the data.

All patients as per inclusion and exclusion criteria as described above will be included in the study. The CT scan (non contrast computed tomography) will be done on (machine parameters at Ganga ram). Only patients with radioopaque stones will be included. Patients falling into the inclusion criteria will be explained about the study and once they agree to participate in study, randomization will be done. Demographic data including patients' age and comorbid, stone-related data including size, location, laterality and number of stones and duration of symptoms will be recorded. The patient will be given either Capsule Tamsulosin 0.4 mg once daily at night or Tablet Silodosin 8 mg once daily at night based on the group assigned. The patient will also be explained about the reasons for follow up earlier than four weeks including fever, persistent pain or gross hematuria. The patients will be called for follow up at 4 weeks with an X-ray KUB without bowel preparation. We will note if the stone has passed or not.

ETHICAL CONSIDERATION:

The funds for supporting this research will be provided by department of pharmacology and therapeutic FJMU, Lahore. Informed consent will be taken from patients prior to research.

DATA ANALYSIS PROCEDURE:

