Data will be entered and analyzed on SPSS version 22. Percentages and frequencies will be calculated for the demographic variables of the patients. The comparison of the two groups will be made by using T- test. P-value of less than 0.05 will be considered significant and the power used will be 0.80.

RESULTS

Frequency and percentage of demographic data

Variables		Frequency	Percentage	
Gender	Male	105	58.7	
	Female	74	41.3	
Income	Less than	108	60.3	
status	50000			
	50000 -150000	69	38.5	
	Greater than	2	1.1	
	150000			
	Normal	166	92.7	
BMI	Obese	13	7.3	
	None	136	76.0	
Comorbidity	HTN	33	18.4	
	Diabetes	10	5.6	

This information sheds light on the sample population's health and demographic distribution, showing a preponderance of people with normal BMIs and lower income levels, as well as a significant percentage of people without comorbid diseases.

In our study there are total 179 patients out of which 74 are females (41.3%) and 105 males (58.7%).

The income, 108 people, or 60.3% of the total, make less than 50,000Rs in month. Just 2 members, or 1.1 percent, make more than 150,000 monthly, while 69 participants (38.5%) have monthly salaries between 50,000 and 150,000.

13 persons (7.3%) are classed as obese, while 166 people (92.7%) have a normal BMI. These numbers represent a sizable fraction of the sample. In terms of comorbidities, 136 individuals (76.0%) state they have no comorbid conditions. Of the people with comorbidities, 10 (5.6%) had diabetes, and 33 (18.4%) had hypertension (HTN).

[figure not shown]

Figure 1: Pie chart of patients using Silodosin and Tamsulosin (Medicine Advised)

Use of medicine (Figure 1)

Tamsulosin and Silodosin, the two drugs prescribed to a group of patients, are distributed as shown in the pie chart. Of the patients, 43% were advised to take Tamsulosin, which is shown as the blue section on the chart. And (57%) of the patients were advised to take silodosin, as shown by the red segment.

Table2: Patient demographic characteristics and study variables are

Varibales	Tamsulosin	Silodosin	p-value	
Body Mass index	Normal	72(43.4%)	94(56.6%)	0.730
	obese	5 (38.5%)	08(61.5%)	
Laterality	Right	65(55.6%)	52(44.4%)	0.001
	Left	12(19.4%)	50(80.6%)	
Symp To CT	Less than 1 week	67(64.4%)	37(35.6%)	
	More than 1 week	10(15.2%)	56(84.8%)	0.001
	More than 2 week	0 (0.0%)	09(100%)	
Posl n Ureler	Proximal	28(51.9%)	26(48.1%)	

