	Mid	08(17.4%)	38(82.6%)	0.001
	Distal	41(51.9%)	38(48.1%)	
Water intake	Less than 1 litre	59(54.6%)	49(45.4%)	
	More than 1 litre	18(25.4%)	53(74.6%)	0.001
Analgesic requirement	Yes	26(61.9%)	16(38.1%)	0.005
	No	51(37.2%)	86(62.8%)	
Time for removal	Less than 14 days	6(10.3%)	52(89.7%)	
	14-21	14(27.5%)	37(72.5%)	0.001
	22-28	57(81.4%)	13(18.6%)	

presented as frequency and percentage with association

The table compares several factors along with the corresponding p-values to assess statistical significance between two drugs tamsulosin and silodosin.

First, based on Body Mass Index (BMI), 43.4% of those with a normal BMI were prescribed Tamsulosin, while 56.6% were recommended Silodosin. On the other hand, among those who were obese, 38.5% were given Tamsulosin and 61.5% were given Silodosin; p-value came out to be 0.730, which meant that there was no statistically significant variation in the medication preferences according to BMI.

15.2% of patients who had pain for more than a week prior to CT scan, received Tamsulosin while 84.8% received silodosin.

51.9% of the patients with proximal ureteric stone were given Tamsulosin and 48.1% received Silodosin.

82.6 percent of patients with mid-ureteric stone problems received Silodosin, while 17.4% received Tamsulosin.

51.9% of patients with distal ureteric stones received Tamsulosin and 48.1% on Silodosin.

Only 38.1% of patients on Silodosin required analgesics, whereas 61.9% of patients on Tamsulosin used analgesics.

89.7% of patients on silodosin had their stone removed in less than 14 days, while only 10.3% of the patients on Tamsulosin had their stone removed in aforementioned duration.

72.5% of patients on Silodosin had their stone removed in 14-21 days, while only 27.5% of the patients on Tamsulosin had their stone removed in same duration.

Moreover, 81.4% on Tamsulosin had their stone removed in 22-28 days and 18.6% patients on Silodosin had it removed in same duration.

		Tamsulosin	Silodosin	p- value
Side	None	61 (40.1%)	91(59.9%)	
effect	Othostatic	09 (60.0%)	06(40.0%)	
	hypotension			0.3.15
	Abnormal	2(66.7%)	1(33.3%)	
	ejaculation			
	Headache	5(55.6%)	4 (44.4%)	

Table 2 Association between Tamsulosin and Silodosin with side effects

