Only a very tiny percentage of patients reported experiencing abnormal ejaculation; 2 individuals on tamsulosin (66.7%) and 1 patient on silodosin (33.3%) reported this side event. Again, this points to an increased chance of this specific adverse effect in Tamsulosin users, but the numbers are too low to make any firm conclusions. Another side effect that was identified involved headaches, which were seen by 4 individuals on silodosin (44.4%) and 5 patients on tamsulosin (55.6%). Headaches were marginally more common among Tamsulosin users compared to Silodosin users, similar to orthostatic hypotension.

Many urologists agree when it comes to the incidence of retrograde ejaculation that it is an indication of therapy efficacy rather than a negative effect. It seems that silodosin relaxes the smooth muscles in the genital and lower urinary tracts sufficiently to cause a retrograde ejaculation. Retrograde ejaculation was more common in the individuals who experienced the most alleviation from lower urinary tract symptoms, which was consistent with this conclusion. This finding implies that the retrograde ejaculation is, in fact, a passive marker of the smooth muscle relaxation brought on by silodosin(32).

Typically, nonselective $\alpha 1$ adrenoceptor antagonists such doxazosin and terazosin are linked to orthostatic hypotension. Nonetheless, in clinical trials, silodosin was linked to a modest incidence of orthostatic hypotension. According to the combined analysis of the US and European studies, 1.1% of patients receiving a placebo and 1.3% of patients receiving silodosin experienced orthostatic hypotension(48).

When compared to Tamsulosin, Silodosin is linked to a larger incidence of retrograde ejaculation but a reduced incidence of peripheral vasodilation-related adverse effects, such as orthostatic hypotension and dizziness, according to a retrospective review conducted by Imperatore et al(49).

In our study comparing the effects of Tamsulosin and Silodosin on patients, it was discovered that only 38.1% of those receiving Silodosin needed analgesics to ameliorate ureteric pain. On the other hand, 61.9% of patients receiving Tamsulosin required analgesic intervention, which is a far larger percentage. This significant difference raises the possibility that silodosin is more successful in treating ureteric stones and it also lowers their need for extra painkillers.

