Similar results were seen in another study showing that, individuals receiving just tamsulosin treatment needed a greater average analgesic dosage of 391.43 \pm 165.60 mg with a p-value of 0.005, which denotes substantial significance, the necessary(50).

Similarly, a study showed statistically significant difference in the amount of analgesics needed by patients treated with Silodosin compared to those treated with tamsulosin only. The robustness of the conclusion was highlighted by the fact that the group receiving Silodosin treatment required considerably fewer analgesics than the groups receiving Tamsulosin, with a p-value of < 0.001(51).

Conclusion

An effective treatment for ureteral stones is medical expulsive therapy. According to our findings, silodosin has a safer profile and is more successful than tamsulosin at ejecting ureteric stones.

Silodosin had an increased rate of stone expulsion and took less time in stone expulsion compared to those treated with Tamsulosin.

In addition, patients treated with silodosin reported fewer side effects, such as a retrograde ejaculation, orthostatic hypotension and headaches as compared to those taking Tamsulosin.

In addition, those who received Silodosin needed less analgesic medication than those who received Tamsulosin.

•

REFERENCES

- Ahmed AFAM, Al-Sayed AYS. Tamsulosin versus Alfuzosin in the Treatment of Patients with Distal Ureteral Stones: Prospective, Randomized, Comparative Study. Korean J Urol. 2010 Mar;51(3):193–7.
- 5. Pietropaolo A, Proietti S, Geraghty R, Skolarikos A, Papatsoris A, Liatsikos E, et al. Trends of 'urolithiasis: interventions, simulation, and

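### The Conclusion's claim that silodosin patients needed less analgesia rests on an unplanned yes/no item, compared without adjustment between arms that differed greatly at presentation

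*Combined protocol and SAP*

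**What the plan says.** The first objective is general: "To evaluate and compare the efficacy and safety of medical expulsive therapy containing tamsulosin and silodosin, specifically". The second concerns side effects. Neither names analgesic use, and the operational definitions cover only stone clearance, ancillary procedures and side effects. Under Data collection and procedure, besides age and comorbidity, "stone-related data including size, location, laterality and number of stones and duration of symptoms will be recorded", and at 4 weeks the only outcome to be noted is whether the stone has passed. On treatment other than the two drugs, that section says "Our study will not change any standard process in place except the randomization between Tamsulosin and Silodosin". The Data analysis procedure names a t-test and no adjusted analysis.

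Analgesic requirement first appears in the Results table of demographic characteristics and study variables, as yes/no by arm with p = 0.005. The text below the table reads it this way: "Only 38.1% of patients on Silodosin required analgesics, whereas 61.9% of patients on Tamsulosin used analgesics". The Discussion repeats those percentages, says the analgesics were for ureteric pain, and adds that silodosin may be more successful and that "it also lowers their need for extra painkillers". The Conclusion lists the finding as a further benefit: "those who received Silodosin needed less analgesic medication than those who received Tamsulosin".

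The same table shows the arms differing in time from symptoms to CT. The text reports that "15.2% of patients who had pain for more than a week prior to CT scan, received Tamsulosin while 84.8% received silodosin". Stone position, laterality and water intake also differ, each with a printed p of 0.001.

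**The concern.** Three things weaken the sentence in the Conclusion.

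- **It was not planned.** Analgesic use was neither a stated outcome nor a stated data item. It was picked out after the table had been made.
- **It is a claim about amount.** The table holds only whether a patient used analgesics. It gives no number of doses and no period, and does not say whether the answer refers to presentation or to the four weeks of treatment.
- **The comparison is crude.** The arms differ strongly in how soon after symptom onset patients were scanned. This could plausibly affect who was given pain relief, whichever study drug was taken.

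The printed percentages add to this. Read as arm rates, they suggest that nearly two thirds of tamsulosin patients needed analgesia, when about one third did. A reader would leave with an unsupported secondary benefit for silodosin, and with a wrong idea of how common analgesic use was.

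**Working it through.** **Inputs, all from the Results table of study variables**

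- Analgesic use yes/no: tamsulosin 26/51, silodosin 16/86. The arm totals are therefore 77 and 102, which sum to the 179 patients reported.
- Symptoms to CT under 1 week: 67 and 37. Over 1 week: 10 and 56. Over 2 weeks: 0 and 9. Later presenters are therefore 10 and 65.
- Two-sided tests are assumed, because the plan does not state sidedness.

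**1. The printed p-value.** Pearson chi-square without continuity correction:

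179 × (26×86 − 51×16)² / (77 × 102 × 42 × 137) = 7.99, p = 0.0047.

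This rounds to the printed 0.005. A pooled t-test gives 0.0045, Fisher's exact test 0.007 and the Yates correction 0.008. The test itself is not at fault.

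**2. The percentages.** There are 26 + 16 = 42 users.

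- Shares of users, as printed: 26/42 = 61.9% and 16/42 = 38.1%.
- Arm rates: 26/77 = 33.8% and 16/102 = 15.7%, a difference of 18.1 points (95% CI 5.4 to 30.8).
- Risk ratio: 0.3377/0.1569 = 2.15. The standard error of its log is √(1/26 − 1/77 + 1/16 − 1/102) = 0.280, so the 95% CI is 1.24 to 3.72.

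**3. The imbalance.** Under 1 week: 67/77 = 87.0% against 37/102 = 36.3%. On the three-level table chi-square is 47.1, p about 6×10⁻¹¹.

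**4. What the imbalance could do.** The documents do not cross analgesic use with symptom duration, so an adjusted estimate cannot be computed. Let R be the assumed ratio of analgesic use in early presenters (under 1 week) to later presenters, the same in both arms. The imbalance alone then produces a risk ratio of

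B(R) = [1 + 0.870(R − 1)] / [1 + 0.363(R − 1)],

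and the ratio left over is 2.15/B(R). For the share of the gap explained, set the later-presenter risk b so that 104Rb + 75b = 42 (104 early and 75 later presenters in all), then compare the expected arm difference with 18.1 points. At R = 3, for example, b = 42/387 = 10.9% and the early risk is 32.6%. The expected arm rates are 29.7% and 18.7%, a gap of 11.0 points, or 61% of 18.1.

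| R (assumed) | B(R) | Ratio left (approx. 95% CI) | Share of gap explained |
|---|---|---|---|
| 1.5 | 1.21 | 1.77 (1.02 to 3.07) | 26% |
| 2 | 1.37 | 1.57 (0.91 to 2.71) | 42% |
| 3 | 1.59 | 1.36 (0.78 to 2.34) | 61% |
| 5 | 1.83 | 1.18 (0.68 to 2.04) | 79% |
| 10 | 2.07 | 1.04 (0.60 to 1.80) | 95% |
| about 14 | 2.15 | 1.00 (0.58 to 1.73) | 100% |

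The intervals carry over the crude variance and are approximate. The lower limit reaches 1 where B(R) = 1.244, which is R of about 1.6.

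**5. Full explanation.** Solving 67a + 10b = 26 and 37a + 65b = 16 gives a = 1530/3985 = 38.4% and b = 110/3985 = 2.8%, a ratio of 13.9. As R grows, B(R) tends to 0.870/0.363 = 2.40, which exceeds 2.15. A full explanation is therefore arithmetically possible, but only with a very strong link.

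**The case against.** A reader might infer that no drug effect is needed to explain the gap. The documents do not support that. Two equations in two unknowns always fit exactly. What matters is whether the solution is plausible, and here it implies about 2 users among 75 later presenters and a ratio near 14. No passage gives any figure for the link between symptom duration and analgesic use. At more moderate ratios part of the gap remains.

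A reader might also divide users by time to stone removal, since silodosin patients are reported to have passed stones sooner. That does not show confounding. Time to removal arises after randomisation, and if the drug shortens it, less analgesia is part of the drug's effect.

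Other points in the report's favour stand:

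- The Discussion gives the indication as ureteric pain, so the indication is not missing from the report.
- The Discussion introduces its efficacy inference as a possibility. Only the Conclusion is wholly unhedged.
- Both arms were treated in one outpatient department under an unchanged standard process. Different prescribing by arm is possible, but nothing documents it. Blinding is not described, which is not the same as being stated to be absent.
- The imbalances bear on every comparison in the report, not on this one alone.

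These points limit what can be said against the result. None of them supplies a planned outcome, a measure of amount or an adjusted comparison.

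**Conclusion.** The concern holds in a bounded form. The crude difference is real as arithmetic: 33.8% against 15.7%, p = 0.005. It comes from an unplanned yes/no item in arms that differ by about 51 percentage points (87.0% − 36.3%) in early presentation. A modest link between early presentation and analgesic use, a ratio of about 1.6, already removes significance. Ratios of 3 to 5 explain about 61% to 79% of the gap, and only about 14 explains all of it. The imbalance could therefore account for much or all of the difference, and the difference cannot be attributed to the drug. This does not show that silodosin has no effect on analgesic need.

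The range assumes the same ratio in both arms, and uses symptom duration alone split at 1 week. Stone position, laterality and water intake could change it in ways the published tables do not allow to be checked. The misreading of 61.9% and 38.1% as arm rates is certain and needs no assumption.

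**What to change.** - **Conclusion:** remove the analgesic sentence, or restate it as an unplanned, unadjusted observation about the proportion of patients using any analgesic.
- **Discussion:** remove the inference that silodosin lowers the need for painkillers.
- **Results and Discussion:** replace 61.9% and 38.1% with 26/77 = 33.8% and 16/102 = 15.7%.
- **Results:** label analgesic use as exploratory and show it by arm within symptom-duration strata (under 1 week; 1 week or more). The early stratum, 67 against 37 patients, is usable. The later one has only 10 tamsulosin patients against 65 on silodosin, and the report should say that it can carry little weight.

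The cost is some rewording and one cross-table. Both variables have already been tabulated by arm, so the patient-level data are presumably still held. The sponsor gives up a favourable secondary claim. The cross-table would address symptom duration only, so the unadjusted label should stay whatever it shows.
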